4.1. Study Design

This is a multi-center, single arm, prospective, observational registry of the SOFIATM/ SOFIATM PLUS Catheter in Europe. Consecutive patients presenting within 6 hours of symptom onset with an anterior circulation large vessel occlusion (LVO) acute ischemic stroke (within the internal carotid artery and internal carotid terminus, middle cerebral $-M_1/M_2$ segments) will be treated using aspiration thrombectomy as first intention and site routine practice. Devices received CE-mark and will be used according to the 'Instructions For Use'.

The follow-up visits will occur at 24 + - 12 hours, at patient discharge, and 90 + - 14 days post-procedure.

Furthermore the study design is adaptive, prospectively stating interim analyses with specified stopping rules, which allow for the possibility of the study to terminate early based on either a determination of study success or of the futility to continue further enrollment.

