5.2. Informed Consent

Image data acquisition, treatment via interventional procedure with a CE-marked device and clinical evaluation are all considered standard of care and thus there is no need for additional consent. Informed consent for data collection must be obtained prior to enrollment of patients in this study and data transmission.

However, most patients will be unable to give their consent prior to treatment. We expect that approximately 60% of patients will be unable to give informed consent prior to therapy with the SOFIA[™]/ SOFIA[™] PLUS catheter. Excluding this group of patients from the study would entail severe scientific and clinical drawbacks. Results would be biased by systematically excluding more severe strokes and patients with aphasia, i.e. mostly left hemispheric strokes. As a consequence, the generalizability of the study results would be limited.

Once the patient's potential eligibility has been determined, the Investigator will discuss the study and ask the patient, or the patient's legally authorized representative, based on the site routine practice and regulatory requirements, if they are interested in participating in the data collection. The study will be explained to the consenting person in lay terms. Study personnel should document the consent process in the participant's medical record per Good Clinical Practice (GCP). The participant or legally authorized representative is to be provided a copy of the signed ICF. In case the patient was not able to provide his consent before the procedure, all attempts will be made to obtain his consent before discharge. Additionally, patients who signed an Informed Consent Form but did not meet general inclusion/exclusion criteria should also be recorded in the screen failure log.

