5.4. Enrollment

Once all inclusion/exclusion criteria are met, the patient is enrolled when a SOFIA[™]/ SOFIA[™] PLUS Catheter is inserted in the patient and will be assigned a five digit identification number (participant study number). The first two digits assigned represent the site identification, followed by a hyphen and three subsequent digits which represent the sequential enrollment number. For example, ID: 04-002 would represent the second participant enrolled at site 04.

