Informed consent has to be obtained prior to enrolment of patients in SESAME. In the normal case written consent will be given by the patient after detailed information about the clinical trial by the investigator. The investigator or sub-investigator will explain the study in detail including risks and benefits for the patient, financing of the study and potential conflicts of interest. Furthermore, the investigator will clarify that the patient or his/her legal guardian will document his/her agreement to participate in the SESAME study by signing the informed consent form.

However, given the sample to be studied (i.e. acute stroke patients showing neurological deficits that may comprise aphasia or disturbance of consciousness) we expect that a certain proportion of patients (estimated 60%) will be unable to give informed consent. Excluding this group of patients from the clinical trial would entail severe scientific and clinical drawbacks. Results would be biased by systematically excluding more severe strokes and patients with aphasia, i.e. mostly left hemispheric strokes. As a consequence, the generalizability of the study results would be limited. Strictly speaking, in case of a positive result this could not be transferred to the patients excluded from the trial (e.g. aphasic patients). This large group would still be excluded from this effective treatment.

A possible solution would allow the *enrolment of patients unable to give informed consent* based on their alleged will following pre-specified criteria. These criteria would have to consider a potential individual benefit as well as any possible risk of participation in the clinical trial. In general the protection of the patient and his autonomy has to be weighed against the potential individual benefit as well as the scientific interest. Following European and national regulations the enrolment of patients (temporarily) unable to give informed consent into clinical trials is possible in an emergency situation if a legal guardian is available and – after careful consideration of possible risks and potential individual benefit – a participation in the clinical trial would comply with the patient's presumptive will. Moreover, standard treatment following best medical practice must not be withheld to the patient by enrolment in the clinical trial.

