For patients eligible for enrolment in SESAME best medical practice in these patients usually comprises the use of CT to rule out hemorrhage or prove ischemic infarction followed by an interventional procedure (thrombectomy), hospitalization and monitoring in a specialized stroke unit. Additional standard treatment consists of supervision and modification of physiological parameters (such as blood pressure, body temperature, blood glucose) and early secondary prevention (e.g. Aspirin).

Suggestion for enrolment of patients unable to give informed consent in SESAME:

[figure not shown]
- A Patient is able to give informed consent and able to provide written consent:
 - Patient is informed by investigator, patient information is handed over to the patient, and patient provides written consent. This may occur prior to treatment or after treatment if the patient was unable to give informed consent and underwent standard of care treatment in agreement with the protocol.
- B Patient is unable to give informed consent, legal guardian is available

Legal guardian acts on behalf of the patient; legal guardian is informed by investigator, patient information is handed over to the legal guardian, legal guardian provides written consent

C –Patient is unable to give informed consent; legal guardian is not available, enrolment of patient by consensus between investigator and independent physician

If the patient is unable to give informed consent and no legal guardian has been appointed, the patient may be enrolled by consensus between the investigator and an independent physician about an the presumed will of the patient; if possible, patient's next of kin should be contacted to appraise the patient's presumed will; the decision has to be documented using a special form. Immediately parallel an application for appointing a legal guardian will be started later patient or legal guardian will be informed by the investigator and may or may not provide written consent. Enrolment through the independent physician will be included to minimize selection bias.

Figure 1: "Overview of Ways of Obtaining Informed Consent"

These options for obtaining the informed consent are NOT equal or interchangeable. The highest priority will always be to obtain informed consent by the participant himself. Only if this option is not possible, other ways may be approached.

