Data collection will not start prior to informed consent but may be done retrospectively. All information and data are subject to medical professional confidentiality, including patient's names, other confidential data as well as sensitive medical information. Data sent to Study Coordinator or Core Labe concerning participants or their participation in this study will be considered confidential. All information and data captured in EDC system or sent to Study Coordinator will be deidentified information. All data used in the analysis and reporting of this evaluation will be used in a manner without identifiable reference to the participant. The Principal Investigator consents to visits by the staff of the Sponsor and its authorized representatives as well as regulatory authorities, which governs the conduct of clinical investigations.

Data will be fully anonymized as soon as legally and practically (for study purposes) possible.

Study Financing and Conflicts of Interest

Financial support for the SESAME study will be pro MicroVention Europe, a French limited liability company, with capital of 40 000€, registered with the Registry of Commerce and Companies in

Versailles under number 440 775 674 RCS, with registered address at [name], [name], France.

The financing of the study will provide case fees to reimburse investigators and study nurses for data collection at the study sites as well as central administrative costs such as project management, study monitoring, data managment, CEC meetings etc.. Study participants will not be reimbursed or receive any other incentives for study participation. Similarly, investigators will not receive any incentives for enrolling participants into the study.

MicroVention Europe will have no access to the study participant data and will not be involved in patient recruitment, study design or analysis and interpretation of the data. However, the Study Coordinator will provide regular updates about the study progress including fully anonymized patient statistics to MicroVention Europe.

Publication of study results will disclose financial support.

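### The protocol's rules on enrolment and consent do not fit together: entry can wait for recovery, and no count of treated but unentered patients is required, so a cohort called consecutive can lose early deaths and lasting incapacity

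*Protocol*

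**What the plan says.** **Timing of entry.** Section 10.3.1 states: "Informed consent has to be obtained prior to enrolment of patients in SESAME"; section 5.2 has the same rule. Section 5.4 says that, once the criteria are met, "the patient is enrolled when a SOFIA" or SOFIA PLUS catheter is inserted. Route A in 10.3.1, the patient's own written consent, then allows: "This may occur prior to treatment or after treatment if the patient was unable to give informed consent and underwent standard of care treatment". Section 10.3.1 adds: "Data collection will not start prior to informed consent but may be done retrospectively".

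**Patients who cannot consent.** Section 5.2: "We expect that approximately 60% of patients will be unable to give informed consent prior to therapy with the" device. For a patient who could not consent beforehand, "all attempts will be made to obtain his consent before discharge"; section 5.9 places the discharge visit at 7±3 days. Section 10.3.1 also offers route B (a legal guardian signs) and route C (the investigator and an independent physician agree on the presumed will). Route C is included expressly to limit selection bias. It is worded as an option, and the patient's own consent always ranks first. Under 8.1, patients who have not agreed to circulation of their pseudonymized data are left out.

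**Denominator and tracking.** Section 4.1 describes "Consecutive patients presenting within 6 hours of symptom onset", and 4.3 also calls the patients consecutive. The ITT sample in 9.2.1 is everyone enrolled. On the screen failure log, 5.2 says that "patients who signed an Informed Consent Form but did not meet general inclusion/exclusion criteria should also be recorded in the screen failure log". No section asks for a count of patients treated with the device but never entered.

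**The concern.** The primary result is a single proportion from a single-arm cohort, so its validity rests on the completeness of that cohort. If a site may wait until a patient can sign, entry depends on early recovery, and early recovery is plausibly tied to mRS at 90 days. A patient who dies on day 2, or never regains capacity, may not appear at all. The mRS 0-2 rate would then be too high, and mortality and symptomatic haemorrhage too low. The confidence interval would not show this, and a larger sample would not cure it. Sections 5.2 and 10.3.1 themselves warn that leaving out severe and aphasic strokes would bias the results.

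This cannot simply be left to an analysis plan, because an analyst cannot recover a count that sites were never told to keep.

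**Working it through.** **Step 1. The rules side by side.** Take a patient who cannot consent, receives the device, and signs on day 5.
- Under 5.4 the patient was enrolled on day 0, at insertion.
- Under 5.2 and 10.3.1 enrolment cannot precede consent, so it falls on day 5 at the earliest.
- Under route A, consent on day 5 is allowed.

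These three cannot all hold unless route B or C was completed before insertion. Now let the same patient die on day 2 with neither B nor C used. By 5.4 the patient is enrolled and belongs in the ITT sample with mRS 6. By 5.2, 8.1 and 10.3.1 the patient is not in the study. The denominator is undefined for exactly this patient.

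**Step 2. Would the planned analysis cover it?** Section 9.2.2 handles missing mRS by multiple imputation, worst case and best case, but only for patients lost to follow-up. Patients never entered are outside it.

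**Step 3. The plan's own precision figure (9.1).** Half-width = 1.96 × √(p(1−p)/n), with p = 0.326.
- n = 236: 1.96 × √(0.326 × 0.674 / 236) = 5.98 points. The stated ±6.0 reproduces.
- 250 with 5% lost: 250 × 0.95 = 237.5, giving 5.96 points. This also agrees.

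**Step 4. Bias from unentered patients.** Inputs from the protocol: p = 32.6% (9.1), taken here as the true rate in all treated patients, and 60% unable to consent beforehand (5.2, 10.3.1). Assumptions, since neither value is in the documents: x, the share of that 60% never entered, and g, their true mRS 0-2 rate.

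Share of all treated patients missing: m = 0.6x. Observed rate = (p − m·g)/(1 − m).

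| x | m | g = 0% | g = 10% | g = 20% |
|---|---|---|---|---|
| 10% | 6% | 0.326/0.94 = 34.7% | 0.320/0.94 = 34.0% | 0.314/0.94 = 33.4% |
| 20% | 12% | 0.326/0.88 = 37.0% | 0.314/0.88 = 35.7% | 0.302/0.88 = 34.3% |
| 30% | 18% | 0.326/0.82 = 39.8% | 0.308/0.82 = 37.6% | 0.290/0.82 = 35.4% |

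**Step 5. When does the bias equal the planned half-width?** Setting the bias to 6 points gives m = 0.06/(0.386 − g).
- g = 0: m = 15.5%, or 15.5/60 = 26% of those unable to consent.
- g = 10%: m = 21.0%, or 35% of them.
- g = 20%: m = 32.3%, or 54% of them.

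At the other end, if only 2% of all treated patients are missed, the bias is at most 0.326/0.98 − 0.326 = 0.7 points.

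**Step 6. Direction.** Bias = m(p − g)/(1 − m). It is upward when the missing patients do worse than 32.6% and downward when they do better. Death is mRS 6, so early deaths have g = 0.

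**The case against.** The best defence is that the protocol foresaw the problem. Routes B and C exist for patients who cannot consent, the synopsis makes presumptive will an inclusion route, 4.3 accepts a signature from a representative or independent physician, and a route C decision is recorded on a special form. If sites use B or C before insertion, 5.4 and the consent rule agree and little is lost. The consent overview figure in 10.3.1 is not shown in the copy reviewed and may fix the order or timing. This stands as mitigation. It does not settle the matter, because the text permits B and C without requiring them at the procedure, ranks the patient's own consent first, and expressly accepts that consent after treatment.

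Three stronger readings are tempting, and the documents do not support them.
- A reader might infer that the screen failure log holds only patients who signed consent. Section 5.2 says such patients should also be recorded, so other entries are implied. The log's full content is simply not defined.
- A reader might infer that unentered patients leave no trace at all. The consent process goes into the medical record, and route C has its own form. What is missing is a required count.
- A reader might infer that every unentered patient inflates the result. Someone who personally declines after treatment has capacity and may have recovered well; losing such patients lowers the observed rate.

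**Conclusion.** The point holds as a conflict of rules together with a missing count. The sections on consent and enrolment do not agree on when a patient enters, one permitted reading lets entry depend on early recovery, and nothing required would show how many treated patients were left out. Upward bias is expected for early deaths and likely for lasting incapacity; decliners may offset part of it.

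The size is unknown. For 10% to 30% of the incapable group missing and a good-outcome rate of 0% to 20% among them, 32.6% would be observed as anything from 33.4% to 39.8%, a bias of 0.8 to 7.2 points against a planned half-width of 6. The upper end needs both the largest assumed loss and no good outcomes among the missing. If few are missed, the effect is under a point. The documents do not show that the bias will occur, only that the stated rules allow it and would not reveal it.

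**What to change.** 1. Reconcile 5.2, 5.4 and the consent text of 10.3.1 into one entry point that does not depend on later recovery, and state how a treated patient who dies or stays incapable before consent is counted in the ITT sample of 9.2.1.
2. Have each site keep an anonymous count of all eligible patients in whom SOFIA or SOFIA PLUS was inserted, with consent route and timing and, for those not entered, the reason (died, no consent obtained, declined), as far as ethics rules allow.
3. Report the count as a flow diagram, with a sensitivity analysis over a range of outcome rates for the unentered patients rather than the worst case alone.

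A fixed deadline for using route B or C, such as 24 hours, is not proposed: it could conflict with the priority that 10.3.1 gives to the patient's own consent.

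Cost: a small workload per site and an ethics committee amendment. Because the change touches the consent pathway, it may need full approval rather than the abbreviated route that 10.3.2 reserves for administrative changes. Treatment is unaffected.

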10.3.2. Protocol Amendment and Modifications

All items in this protocol are to be followed exactly. If an amendment is required, this must be made in written form and receive approval from all persons and authorities who approved the original protocol. Administrative changes (not affecting participants' benefits/ risks ratio) may be inserted with abbreviated approval by the EC/ IRB. Major amendments require full approval of the EC/ IRB and Study Coordinator prior to implementation, except in emergency situations. All amendments will be distributed to all protocol recipients with instructions. Documentation of all correspondence regarding protocol amendment study activity should be forwarded to the Study Coordinator.

In situations requiring departure from the protocol, the investigator or other physician in attendance will contact the Study Coordinator. If possible, this contact will be made before implementing any departure from the protocol. In all cases, contact with the Study Coordinator must be made as soon as possible in order to discuss the situation and agree on an appropriate course of action. The protocol deviation eCRF and source document will describe any departure from the protocol and the circumstances.

It is the responsibility of investigators to inform their EC/ IRB of all protocol amendments or modifications and protocol deviations as required by their EC/ IRB procedure and country law.

10.4. Clinical Events Committee

The Clinical Events Committee (CEC) is made up of independent medical doctors who are not participants in the study. At the onset of the study, the CEC will establish explicit rules outlining the minimum amount of data required, and the algorithm followed in order to classify a clinical event. All members of the CEC will be blinded to the primary results of the trial. The CEC will meet regularly to review and adjudicate any clinical events, to evaluate their relationship to the de-

vice/procedure and to the study endpoints. The CEC will also review and rule on all deaths that occur throughout the trial. A CEC Charter, generated by the CEC membership will identify the frequency of meetings, identify criteria for early review safety, any additional criteria for stopping the study early and criteria for inactivating sites for excessive protocol deviations.

